Follow-up Period: All patients who complete or prematurely discontinue the treatment will be assessed for safety, laboratory, and clinical assessments 12 weeks after the end of treatment. At the end of the 12-week follow-up period, patients who passed a DBPCFC of at least 444 mg (cumulative) at week 24 will undergo a final DBPCFC (up to 2044 mg cumulative), under intensive monitoring, at week 36 to assess the level of peanut sensitivity after 12 weeks off dupilumab to determine whether there is evidence of persistent effects and sustained unresponsiveness.

Study Duration	The duration of the study for a patient is approximately 36 weeks, excluding the screening period.
End of Study Definition	The end of study for this study is defined as the last visit of the last patient.
Population	
Sample Size:	Approximately 24 patients.
Target Population:	Male and female pediatric patients ages 6 to 17 years with a history of peanut allergy confirmed by peanut SPT, sIgE and by the amount of peanut protein (mg) safely ingested during a peanut DBPCFC.
Treatment(s)	
Study Drug	Dupilumab
Dose/Route/Schedule:	200 mg or 300 mg SC Q2W (weight based) following a loading dose of 400 mg or 600 mg, respectively, on day 1.
Endpoint(s)	
Primary:	
 Proportion of patients treated with dupilumab that pass a DBPCFC with at least 444 mg (cumulative) peanut protein at week 24
Secondary:	
 Change in the cumulative tolerated dose (log transformed) mg of peanut protein during a DBPCFC from baseline to measured DBPCFC visits at weeks 24 and 36. Proportion of patients treated with dupilumab that pass a DBPCFC with at least 444 mg (cumulative) peanut protein at week 36. Proportion of patients treated with dupilumab that pass a DBPCFC with at least 1044 mg (cumulative) peanut protein at weeks 24 and 36. Proportion of patients treated with dupilumab that pass a DBPCFC with 2044 mg (cumulative) peanut protein at weeks 24 and 36. Percent change from baseline in sIgE to post-baseline visits (weeks 4, 8, 12, 24, and 36) Change from baseline in titrated SPT at week 4, 12, 24, 36 as measured by the average wheal size AUC after peanut allergen stimulation at different concentrations. Proportion of patients with Grade II or above allergic reactions during the DBPCFC at week 24 Proportion of patients using epinephrine as a rescue medication during the DBPCFC at week 24

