Double-Blind Placebo-Controlled Food Challenge

At week 24, under intensive monitoring, all patients will undergo a DBPCFC up to 2044 mg peanut protein (cumulative) or placebo (see [Appendix 1](#)) to assess tolerability. The patient's sensitivity to peanut allergen is defined as the dose at which the patient experiences allergic reactions. All symptoms and signs will be evaluated and rated based on a standardized oral food challenge scoring system (see [Appendix 2](#)). Up-dosing during the DBPCFC will be stopped when the blinded assessor finds symptoms and/or signs that indicate a definite objective allergic reaction (CoFAR grading system [see [Appendix 2](#)]) has occurred based on clinically significant changes in reported symptoms, physical findings, or vital signs that the patient is experiencing to the challenge material. Vital signs will be assessed every 15 to 30 minutes. The DBPCFC will consist of 8 doses (peanut protein or placebo), with a dose given every 15 to 30 minutes: 1, 3, 10, 30, 100, 300, 600 mg, and 1000 mg resulting in a total challenge of up to 2044 mg peanut protein (cumulative). Both peanut and oat protein will be concealed in a food that masks the taste. The food challenges will be performed on different days (1 day placebo [oat] protein, 1 day peanut protein, with order determined at random) at least 24 hours but not more than 7 days apart and not within 24 hours of a dose of study drug. Patients will be considered to have passed the DBPCFC if they do not experience any objective Grade 1 reaction by the CoFAR grading system (see [Appendix 2](#)). If the patient experiences reactions, he/she will be treated with the necessary rescue medications. He/she will be observed for a minimum of 2 hours after the final administered dose and discharged only when deemed clinically stable by a study physician. Symptom severity will be adjudicated by an independent, blinded assessor who is not involved in patient study visit conduct ([Bock, 1988](#); [Sampson, 2006](#)).

Study design safety considerations for DBPCFC are described in Section [3.3.2](#).

Post-Treatment Follow-up Period (12 weeks)

All patients will have a 12-week follow-up period after the end of treatment and will undergo safety, laboratory, and clinical assessments.

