8.3.2. Study Drug Discontinuation

Patients who permanently discontinue from study drug and who do not withdraw from the study will be asked to return to the clinic for all remaining study visits per the visit schedule.

Patients who permanently discontinue from study drug and who opt to withdraw from the study will be asked to complete study assessments, per Section 9.1.2.

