3.1. The Safety Analysis Set (SAF)

SAF includes all patients who received any dupilumab. Efficacy, treatment compliance/administration and all clinical safety variables will be analyzed using the SAF.

Efficacy at week 36 (Subset of SAF at week 36) will be analyzed using SAF patients who pass a DBPCFC of at least 444 mg (cumulative) of peanut protein at week 24.

For safety summaries, three analysis periods are defined as follows for SAF:

- Treatment period is defined as
 - Day 1 to the date of second DBPCFC at week 24 EOT visit for those patients who completed week 24 visit with week 24 visit date present
 - Day 1 to the early terminiation (ET) visit date for those patients who early terminated before week 24 visit
- Follow-up period is defined as
 - The day after the week 24 EOT visit date to the date of the end of study visit for those patients who completed week 24 visit with week 24 visit date present
 - The day after the ET visit date during treatment period to the date of the end of study visit for those patients who early terminated in the treatment period
- Overall study period is defined as Day 1 to the date of the end of study visit.

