5.5.2. Exposure to Investigational Product

The duration of treatment exposure during the study in day will be presented and is calculated as:

(Date of last study drug injection – date of first study drug injection) + 14 days

Note: the calculations are regardless of temporary dosing interruption.

Summary of exposure to study drug will include the number of study drug administered and duration of exposure. The duration of exposure during the study will be summarized using number of patients, mean, SD, median, Q1, Q3, minimum and maximum.

In addition, the duration of exposure to study drug will be summarized categorically by counts and percentages for each of the following categories as well:

```
\geq14 days, \geq28 days, \geq42 days, \geq56 days, \geq70 days, \geq84 days, \geq98 days, \geq112 days, \geq126 days, \geq140 days, \geq154 days, and \geq168 days
```

The duration of observation period during the study in day is calculated as:

(Date of last visit – date of first study drug injection) + 1 day

The duration of observation period will be summarized descriptively using number of patients, mean, SD, median, Q1, Q3, minimum and maximum. In addition, the number (%) of patients with observation periods will be presented by specific time periods. The time periods of interest are specified as:

```
<15 days, \geq15 days, \geq29 days, \geq43 days, \geq57 days, \geq71 days, \geq85 days, \geq99 days, \geq113 days, \geq127 days, \geq141 days, \geq155 days, and \geq169 days
```

Listing of dose administration will be presented with information on administration date/time, study day, locations of injections, kit number, and whether or not the total dose is administered for each dose will be presented.

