5.7.1. Adverse Events

The number and proportion of patients reporting TEAEs will be summarized for treatment period and follow-up period separately, as described in Section 3.1.

AE incidence tables will be presented for the SAF as well as subgroups. Summary of TEAEs will present the number (n) and percentage (%) of patients experiencing an TEAE by SOC and PT, sorted by the decreasing frequency of SOC and PT. Multiple occurrences of AEs of the same PT (or SOC) in the same patient will be counted only once for that PT (or SOC). For AE tables presenting severity, the worst severity will be chosen for patients with multiple instances of the

same event. The denominator for computation of percentage is the number of patients for the corresponding analysis period as specified in Section 3.1.

Protocol: R668-ALG-1702

Date: March 3, 2021

An overall summary of TEAEs will be provided with number and proportion of patients with any:

- TEAE
- Serious TEAE
- TEAE/Serious TEAE leading to death
- TEAE/Serious TEAE leading to permanent treatment discontinuation
- Study drug related TEAE/serious TEAE
- Maximum intensity for TEAE

Detailed summaries of TEAEs will include:

- TEAEs
 - TEAEs by primary SOC/PT
 - TEAEs by primary SOC/HLT/PT
 - TEAEs by PT
 - TEAEs by primary SOC/PT with incidence of PT \geq 5%
 - TEAEs by severity and by primary SOC/PT
 - TEAEs related to study drug as assessed by the investigator by primary SOC/PT
 - Severe TEAEs by primary SOC/PT
 - Severe TEAEs related to study drug as assessed by the investigator by primary SOC/PT
 - TEAEs leading to permanent discontinuation of study treatment by primary SOC/PT
- Serious TEAE
 - Serious TEAEs by primary SOC/PT
 - Serious TEAEs related to study drug as assessed by the investigator by primary SOC/PT
 - Time to first occurrence of serious TEAEs
- Death by primary SOC/PT

Number and proportion of patients reporting pre-treatment adverse events will be tabulated by primary SOC and PT.

The number and proportion of patients with injection site reaction by PT will be summarized.

The number and proportion of TEAE per 100 patient-year will be tabulated by primary SOC/HLT/PT. The number of patients with at least one event per 100 patient-year will be calculated and summarized for the following:

Protocol: R668-ALG-1702

Date: March 3, 2021

- TEAE by primary SOC/HLT/PT
- Severe TEAE by primary SOC/HLT/PT
- Serious TEAE by primary SOC/HLT/PT

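### SAP 3.1 splits treatment from follow-up without using the last dose, so post-exposure events in children who stop dupilumab early but stay in the study are tabulated in the treatment period

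*Protocol*

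**What the plan says.** **Period definitions.** SAP 3.1 sets the treatment period as "Day 1 to the date of second DBPCFC at week 24 EOT visit for those patients who completed week 24 visit". For patients who terminate before week 24 it runs to the early termination visit. For the first group, follow-up is "The day after the week 24 EOT visit date to the date of the end of study visit". The date of the last injection appears in neither branch.

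**Visits after stopping drug.** Protocol 8.3.2 deals with patients who stop dupilumab permanently: those "who do not withdraw from the study will be asked to return to the clinic for all remaining study visits per the visit schedule". Protocol 8.7 foresees this case: prohibited medication ends treatment but not study participation.

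**Use of the periods.** SAP 5.7.1: "The number and proportion of patients reporting TEAEs will be summarized for treatment period and follow-up period separately". SAP 4.3 classifies concomitant medications and procedures by the same periods.

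**Exposure.** SAP 5.5.2 computes its duration from the first to the last injection and adds 14 days.

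**Follow-up.** The synopsis, repeated in SAP 2.4, covers patients who complete treatment as well as those who "prematurely discontinue the treatment will be assessed for safety, laboratory, and clinical assessments 12 weeks after the end of treatment". Protocol 6.1 says: "All patients will have a 12-week follow-up period after the end of treatment and will undergo safety, laboratory, and clinical assessments". The Schedule of Events labels the week 24 visit EOT. No passage says what end of treatment means for a child who stops drug early.

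**The concern.** A child who stops dupilumab at week 4 and attends every remaining visit keeps a treatment period that lasts to the second week 24 challenge. An adverse event at week 18 in that child goes into the treatment column, although by the SAP's own formula exposure ended at week 6. In a completer, an event the same number of weeks after the last dose goes into the follow-up column. The by-period tables therefore mix two meanings of treatment period.

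The definition can also fail to give a date. Protocol 6.1.3.1 lists stopping rules that apply to both study drug and food challenge, and the heading of Protocol 8.3.2.1 likewise covers both. A child stopped on those grounds who still attends week 24 may have no second challenge date. The first branch of SAP 3.1 then has no end point, and the second does not apply because the child did not terminate early. Protocol 6.1 says that all patients undergo the week 24 challenge, so the passages do not settle this case.

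With about 24 patients, one or two reallocated events would show in a by-period table.

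**Working it through.** **Inputs.** Schedule of Events: day 1, week 22 on day 155, week 24 on day 169, week 36 on day 253. Last planned dose at week 22 (Protocol 6.1). Exposure formula from SAP 5.5.2. About 24 patients (Protocol 7.1). Challenge days at most 7 days apart (Protocol 6.1).

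**1. Reproduce the planned periods.**
- Treatment: (169 − 1)/7 = 24 weeks. Follow-up: (253 − 169)/7 = 12 weeks.
- Full-course exposure: (155 − 1) + 14 = 168 days.

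For a completer the exposure end and the week 24 visit therefore coincide to within a day, and the two definitions agree.

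**2. Early discontinuer who completes week 24 on day 169.** Last day of exposure = last dose day − 1 + 14. Post-exposure days inside the SAP treatment period = 169 − last day of exposure.

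| Last dose (week) | Study day | Last day of exposure | Post-exposure days | Share of 169 |
|---|---|---|---|---|
| 0 | 1 | 14 | 155 | 92% |
| 4 | 29 | 42 | 127 | 75% |
| 8 | 57 | 70 | 99 | 59% |
| 12 | 85 | 98 | 71 | 42% |
| 16 | 113 | 126 | 43 | 25% |
| 20 | 141 | 154 | 15 | 9% |
| 22 (full course) | 155 | 168 | 1 | 1% |

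A week 24 visit 3 days late and a second challenge 7 days after that would add up to 10 days to each row.

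**3. Same time since dose, different label.** Six weeks (42 days) after the last dose is day 155 + 42 = 197 in a completer, which is follow-up. It is day 29 + 42 = 71 in a child last dosed at week 4, which is treatment.

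**4. Share of treatment-period time.** The documents do not say how many children will stop drug but stay. Assume 2 to 4 of 24, last dosed between weeks 4 and 16, with all 24 children followed to week 24.
- Total: 24 × 24 = 576 patient-weeks.
- Last dose week 4: 24 − (4 + 2) = 18 weeks each. Four children: 72, and 72/576 = 12.5%.
- Last dose week 16: 24 − (16 + 2) = 6 weeks each. Two children: 12, and 12/576 = 2.1%.

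**5. Overlap.** Treatment ends at the second challenge, but follow-up starts the day after the week 24 visit date. If that date is the first challenge day, up to 7 days belong to both periods.

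**The case against.** **The documents do not flatly contradict each other.** A reader might infer that the synopsis and SAP 2.4 start follow-up at each child's own end of treatment, so that SAP 3.1 contradicts them. The text does not go that far. The sentence sets an assessment time and defines no period start, the week 24 visit is itself labelled EOT, and the synopsis ties the end of the 12-week follow-up to week 36. If end of treatment means week 24, SAP 3.1, Protocol 8.3.2 and the schedule agree. This stands. What remains is an undefined term. On the patient-specific reading, a child last dosed at week 10 has exposure to day 84 and ends 12 weeks of follow-up on day 84 + 84 = 168, before SAP 3.1 would start it. That is reason enough to define the term.

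**The reach is narrow.** This also stands. The treatment-emergent period in SAP 4.6.1 covers both treatment and follow-up, so total TEAEs do not change, and efficacy is untouched. SAP 5.7.2 gives no by-period table of events of special interest, and SAP 5.7.1 does not say that rates per 100 patient-years use treatment-period time. Distortion of either might be inferred but is not stated. The planned listings of event dates, action taken with study drug and injection dates let a reader reclassify cases by hand, although the tables would still be mixed.

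**Post-exposure is not drug-free.** Protocol 6.1 bases the 12-week follow-up on the time for drug to fall below quantification after the last dose. If 12 weeks from the last dose is taken as clearance, four children last dosed at week 4 contribute 4 × (24 − 16) = 32 of 576 weeks (5.6%), and two last dosed at week 16 contribute none. The 14 days is an exposure convention, not a washout.

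**The count is assumed.** The planned 15% is dropout and does not estimate children who stop drug but remain. Nor can it be said that they stop mostly for safety reasons: Protocol 8.3.2.1 also lists missed doses and prohibited medication.

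**Conclusion.** The point holds as a minor defect in the descriptive safety tables. SAP 3.1 ignores the last dose, the protocol keeps early discontinuers on schedule to week 24, and TEAEs and concomitant medications are split by period. It follows that their post-exposure events enter the treatment column. A child whose challenge was also stopped may have no defined period end, and the two periods can overlap by up to 7 days.

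Per child, the effect runs from 15 days (last dose week 20) to 155 days (day 1 dose only). For the trial it is about 2% to 13% of treatment-period time under the stated assumption, less if drug clearance is the criterion, and nil if no child stops early and stays. The documents do not support a claim that SAP 3.1 contradicts the synopsis outright, or that these events are all off drug.

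**What to change.** - In SAP 3.1, for patients who permanently stop dupilumab early, end the treatment period at last injection + 14 days and start follow-up the next day. Alternatively, keep the present periods and add an on-treatment TEAE summary on that basis. State that drug may persist beyond this date. The rule uses the SAP's own exposure convention, falls at week 24 for an on-schedule completer (155 + 14 = day 169), and gives an end date when there is no second challenge.
- For completers, start follow-up the day after the second week 24 challenge, so that the periods cannot overlap.
- State what end of treatment means for early discontinuers, and reconcile the synopsis, Protocol 6.1 and SAP 2.4 with Protocol 8.3.2 and SAP 3.1.

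The cost is a SAP definition, some programming and a wording reconciliation. Injection dates are already collected, so no new data are needed. By-period counts would shift slightly for discontinuers, and for completers only where the two periods now overlap.

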1. INTRODUCTION

Food allergy is a potentially life-threatening condition that affects up to 8% of young children and 3% to 5% of the entire United States (US) population (Gupta, 2011) (Sicherer, 2010) (Nwaru, 2014). Unlike many other childhood allergies, peanut allergy typically persists into adulthood and is associated with a higher incidence of severe anaphylaxis as compared with other food allergies (Dyer, 2015). The prevalence of peanut allergy by self-reports in US and European Union (EU) children varies from 1.2% to 2.0% (Dunlop, 2018). The current remedies for food allergy are food avoidance and treatment with medications such as injectable epinephrine for accidental exposures associated with severe allergic symptoms. Although recent progress has been made in the treatment of food allergy through allergen-specific oral immunotherapy (OIT), there is an unmet need for a new therapy in food allergy (Jones, 2009) (Anagnostou, 2011) (Anagnostou, 2014). The aim of OIT is to induce desensitization and increase the threshold for peanut ingestion, and reduce the risks of allergic reactions after accidental ingestion. However, many patients in OIT trials continue to have side effects that can hinder their compliance and the overall efficacy of OIT. There is also a subsequent rapid loss of tolerance upon cessation of OIT (Vickery, 2014) (Wood, 2017).

The immune system in the gut actively induces an immune tolerant state to the proteins that are normally consumed. Food allergy occurs when the body has a break in this tolerance, which results in an abnormal immune reaction to food. It is known that allergic response to food including peanut protein is an immunoglobulin E (IgE) mediated event; however, recent data suggest that interleukin (IL)-4 and IL-13 may also play a significant role in food allergy pathogenesis. Cross-linking of peanut-specific IgE (sIgE) bound to high affinity IgE receptors on mast cells and basophils triggers immediate degranulation. Subsequent release of a diverse array of inflammatory mediators results in severe allergic symptoms such as hives, wheezing, vomiting and, in severe cases, anaphylactic shock. Release of these mediators also initiates IL-4 and IL-13 release, which results in eosinophil gastrointestinal (GI) tissue infiltration and creates a cycle of chronic Type 2 allergic inflammation (Wong, 2016).

Dupilumab, a fully human VelocImmune[®]-derived monoclonal antibody directed against interleukin-4 receptor alpha (IL-4R α), blocks the activity of IL-4 and IL-13 and is approved as a treatment for atopic dermatitis (AD). As of October 2019, dupilumab has been approved for the adult atopic dermatitis (AD) indication in over 40 countries worldwide. Additionally, dupilumab has been approved for severe asthma with type 2 inflammation in both adult and adolescent patients, and recently in adult patients with chronic rhinosinusitis with nasal polyposis (CRSwNP), and adolescents with AD. Dupilumab is also under development for a range of type 2 inflammatory diseases such as food allergies and eosinophilic esophagitis (EOE) amongst others.

This phase 2 proof-of-concept (POC) study will explore whether dupilumab has immunomodulatory effects on Type 2 immune responses, which may result in improved safety and tolerance to peanut exposure as determined by the ability to tolerate a higher cumulative peanut protein dose level during a double-blind, placebo-controlled food challenge (DBPCFC) after 24 weeks of monotherapy treatment. In addition, the study will evaluate whether dupilumab influences known biomarkers important in the allergic response to peanuts such as a reduction in allergen-specific IgE and/or increase in allergen-specific IgG4.

Additional background information on the study drug and development program can be found in the Investigator's Brochure.

2. STUDY OBJECTIVES

2.1. Primary Objective

The primary objective of the study is to assess the tolerability of peanut protein in pediatric patients (6 to 17 years old) treated with dupilumab monotherapy, in which tolerability is defined as the proportion of patients who safely pass a double-blind placebo-controlled food challenge (DBPCFC) at week 24.

2.2. Secondary Objectives

The secondary objectives of the study include:

- To determine whether dupilumab treatment improves peanut tolerability, defined as a change in the cumulative tolerated dose (log transformed) of peanut protein during a DBPCFC (up to 2044 mg cumulative)
- To evaluate the safety and tolerability of dupilumab treatment in peanut allergic patients
- To evaluate the effects of dupilumab treatment on the levels of peanut-specific IgE
- To evaluate the treatment effect of dupilumab on the average wheal size after a titrated skin prick test (SPT), as measured by area under the curve (AUC) of the average wheal size induced by peanut extract at different concentrations.
- To assess the incidence of treatment-emergent anti-drug antibodies (ADA) to dupilumab in patients over time

